**EFFECT OF LIPID INTAKE ON DIRECT HYPERBILIRUBINEMIA IN LATE PRETERM
AND TERM INFANTS WITH GASTROINTESTINAL SURGICAL PROBLEMS**

NCT01555957

I. PURPOSE OF THE STUDY AND BACKGROUND

The purpose of the study is to establish a cause and effect relationship between lipid intake and the incidence of direct hyperbilirubinemia (cholestasis) in late preterm and term infants with major gastro-intestinal (GI) surgical disorders such as gastroschisis, omphalocele, volvulus, TE fistula, duodenal atresia, jejunal atresia, ileal atresia, Hirschsprung's disease, anorectal malformation, intestinal obstruction and GI perforations requiring surgery. Infants with major GI surgical disorders as mentioned above will be randomized to receive 1gm/kg/day or 2gm/kg/day of 20% intralipids within the first 72 hours after birth. The study is not open to all surgical infants because infants with other surgical problems can be fed enterally within few days after surgery and usually do not require TPN for prolong periods (>2 weeks). Also infants with major GI surgical disorders have similar clinical course, undergo similar type of operative procedures, and have similar complications thus eliminating potential confounding factors. The primary outcome measure is the incidence rate of parenteral nutrition associated cholestasis (PNAC). PNAC will be defined as serum direct bilirubin $\geq 2\text{mg/dl}$ in the absence of other known causes of direct hyperbilirubinemia as described under exclusion criteria.

II. BACKGROUND AND JUSTIFICATION:

Since its introduction in the late 1960s, total parenteral nutrition (TPN) has established itself as an effective mode for parenteral hyperalimentation in patients with acute or chronic intestinal failure. Out of the many complications of parenteral nutrition, the most common is the cholestasis often referred to as Parenteral Nutrition Associated Cholestasis (PNAC). PNAC is defined clinically using

direct bilirubin as an index measure in the absence of other known causes of direct hyperbilirubinemia (see exclusion criteria). The reported incidence of PNAC in neonates is as high as 84%. [1, 2]

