4. **Exclusion Criteria:** Neonates with the following condition will be excluded: 1) If does not need TPN by 72 hours; 2) Direct hyperbilirubinemia within the first 72 hours after birth; 3) TORCH infections (Toxoplasmosis, CMV, Herpes, Rubella, HIV, etc); 4) Biliary tract disorders leading to direct hyperbilirubinemia; 5) Known metabolic disorders that may be associated with direct hyperbilirubinemia- such as Galactosemia, α -1 antitrypsin deficiency, etc.

IV. METHODS AND PROCEDURES

a) Study Design: This is a prospective randomized controlled trial s planned in order to evaluate the incidence rate of PNAC between 1gm/kg/day of 20% intralipid and 2 gm/kg/day of 20% intralipid in high-risk neonates \geq 34 weeks gestational age (GA). PNAC will be defined as serum direct bilirubin \geq 2mg/dl in the absence of other known causes of direct hyperbilirubinemia as described in the exclusion criteria.

b) Screening: All neonates \geq 34 weeks GA and admitted to the NICU at URMC with major GI surgical disorders will be screened for study criteria within 72 hours after birth. Infants will be

identified by a designated investigator with regularly scheduled screening of admissions, GA, postnatal days and admission diagnosis. Screening will take place on an ongoing basis and not less than 3 times per week. The screening log will include GA, postnatal days, and type of GI surgical disorders, and whether or not the infant was enrolled in the study. If not enrolled, the reason will be recorded. The number and demographic characteristics of eligible subjects not included will be collected to assess the representation of the sample of subjects included.

- c) Enrollment and Consent:** Families will be approached by one of the investigator as soon as possible after eligibility is ascertained to allow sufficient time for the family to ask questions about the study. Parental consent may be obtained any time during the first 72 hours after birth. Consent will be documented on an IRB approved consent form. Each subject will be assigned a unique study identification number by the investigator after consent is obtained.
- d) Pre-randomization:** Once the infant is enrolled in the study, one of the investigators will notify the Research Pharmacist (RP) by telephone call during working hours (8AM-5PM) for registration and randomization. Information on weight of the infant will be provided to the RP for accurate dosing of intravenous lipid on each day.

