- e) Registration:** A log sheet of subjects registered with their names, study ID numbers, medical record number, dates of birth, and dates of randomization will be kept by the RP
- f) Randomization** will be to two arms: 1g/kg/day intravenous lipid or 2 g/kg/day for 6 weeks or until develops direct bilirubin \geq 2mg/dl (in the absence of sepsis) or reaches enteral feeds and no longer requires parenteral nutrition. A block randomization with 8 subjects in each block will be performed. Study group assignments will be made by the RP with the use of a randomization scheme provided by the biostatistician. The assignment will be 1:1 ratio.

g) Route, Frequency, and Duration: The lipids will be given intravenously every day as per the standard of care for 6 weeks or until reach one of the study end points (reach enteral feeds and no longer require parenteral nutrition or has direct bilirubin ≥ 2 mg/dl in the absence of sepsis). All enrolled infants including those randomized to 2 gm/kg/day intravenous lipid will be started at 1 gm/kg/day of intravenous lipids as per the standard of care on day 2 after birth. The procedures for titrating subjects randomized to the higher dose will be consistent with standard procedures. The daily intravenous lipid intake will be increased to 2 gm/kg/day in those randomized to 2 gm/kg/day. The amount of proteins and glucose will be ordered as per the unit policy and at the discretion of the attending neonatologist.

h) Dose Adjustments: Daily assessment of the weight will be performed by the investigator and will be reported to the RP for appropriate adjustment to the dosing of the intravenous lipid. Each day, the RP will inform the clinical care team of volume of intravenous lipid to be infused over the day. The clinical care team will complete the request in the E-record using the information provided by the investigator or the RP.

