- k) **Primary Outcome Measures:** PNAC will be the primary outcome measure and will be defined as direct bilirubin ≥ 2 mg/dl developing within one week of the completion of 6 week randomization period in the absence of other known causes (discussed earlier). Total serum bilirubin and direct bilirubin concentration will be measured once weekly as part of the standard of care when on parenteral nutrition. The direct bilirubin is usually measured until the resolution of direct hyperbilirubinemia as part of the standard of care. If parents have consented, we will collect blood that is leftover from blood draws that are done as part of standard of care.

The blood samples will be stored in -80 degree freezer in the PI's laboratory within the Department of Neonatology for possible future research on intravenous nutrition and its effects on the liver such as identifying a more sensitive biochemical marker than direct bilirubin concentration of liver injury. Samples will be stored with a study number only and will only be linked to the data collected for the purposes of this study. Only study team members will have access to the stored blood and will be able to use the samples. Future research on stored blood after completion of this study will only be conducted by the PI on IRB approval.

- l) Secondary Outcome measures:** Secondary outcome measures will include peak direct bilirubin concentrations during hospital stay, use of choleretic medications and use of Omegavan during the hospital stay and percentage weight gain during the 6 week study period.
- m) Data Safety Monitoring:** There are several reasons why independent data safety monitoring and stopping rules were not considered for this study as described below:
 - 1) In this study, the outcome measure, direct hyperbilirubinemia $>2.0\text{mg/dL}$, is the potential side effect of interest secondary to intravenous lipid intake. As per the standard of care, the intravenous lipid intake of 1-2 gm/kg/day is routinely used in the presence of direct hyperbilirubinemia of 2 mg/dL to provide essential calories and prevent essential fatty acid deficiency. Usually, choleretic medications such as cholecystokinin are used to resolve PNAC at this point.

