 - 2) Our hypothesis is that the development of PNAC is causally related to the cumulative lipid intake, however, protein and glucose intake may modify the association between lipid intake and PNAC. In addition, sepsis and prematurity are confounding risk factors. The sample size calculated ($n=40$) to evaluate the outcome measure (or the adverse event) accounts for the variable duration of the TPN (cumulative lipid intake) and presence of confounding risk factors. Therefore, meaningful statistical analysis is not possible with an interim analysis of less than 40 subjects.
 - 3) As suggested by our observational study, a mean cumulative dose of 55gm/kg (SD 15) of intravenous lipid is required before the development of PNAC in late preterm and term

infants. Thus, it is expected that an infant on 1gm/kg/day of intravenous lipid arm will take ~ 55 days to develop PNAC. Therefore, considering the fact that TPN intake will often be less than 42 days among study subjects, not all infants in either group are expected to develop PNAC. PNAC, the study outcome, as defined for the purpose of the study, is the earliest when any medications are used to treat PNAC as per the standard of care. Severe PNAC is defined when direct bilirubin concentration is > 10 mg/dL and is very rare. The randomization of intravenous lipid intake will be stopped long before severe PNAC may be seen among enrolled subjects.

- 4) Performing interim analyses will require more stringent significance level which will increase the sample size required to perform the study. This is a pilot study performed as part of fellow's project for which 40 subjects are required for meaningful analysis of outcome (or adverse event)
- 5) This study has been designed as a block randomization with each block having 8 subjects with 1:1 assignment, so even if all enrolled infants were to develop PNAC, it will suggest that there is no difference between the two groups and there is no causal association between intravenous lipid intake and cholestasis.

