Because of reasons mentioned even if the first 20 subjects (50%) hit the direct bilirubin endpoint, interim analysis is unlikely to allow meaningful analysis of the causation between lipid intake and the outcome measure (or adverse event) as provided in the protocol. In other words, it is unlikely to reach adjusted statistical significance required for interim analyses. Thus, since the outcome measure and the adverse event are the same and the sample size required to evaluate the association (or the adverse event) controlling for other factors is 40, no interim analysis and stopping rules were considered for this pilot study. For trial management, the investigation team will track enrollment and protocol compliance and review every 3 months.

V. DATA COLLECTION: The baseline data on demographics and clinical factors (antenatal and postnatal) before randomization on each subject will be collected. Similarly, data on clinical factors will be collected during the 6 week study period or until the subject is receiving intravenous lipid as per

randomization or until the subject develops PNAC (direct bilirubin ≥ 2 mg/dl in the absence of concurrent infection).

The information on TPN components, specifically amount of lipid, protein, and glucose intake on each day will be prospectively collected using pharmacy and TPN records. Information on cumulative amount of lipid intake, cumulative amount of protein intake, and cumulative amount of glucose intake will be determined for all enrolled subjects. The additional information that will be collected is duration (days) of TPN, use of trace elements, duration (days) of NPO, type of enteral feeds (maternal breast milk vs. Formula) duration (days) of antibiotic use, onset and duration of choleric medications, sepsis defined as blood culture positivity or clinical signs and symptoms of sepsis with the use of antibiotics for > 3 days, day of life when the infant reaches an enteral intake of 120 ml/kg/day, duration (days) of mechanical ventilation, duration of CPAP, duration of oxygen supplementation, and amount of erythrocyte transfusions during the study period. However, use of choleric medications and discontinuation of trace elements from the TPN is not expected during the study period based on the unit policy as delineated earlier.

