All statistical analyses will be conducted using Version 10 of the SAS System for Windows (Copyright © 2002-2003 SAS Institute Inc., Cary, NC, USA.) by a biostatistician. Descriptive statistics will be used to summarize outcomes by treatment groups. For continuous variables, descriptive statistics will include the mean, median, standard deviation, minimum, maximum, number of available observations, and number of missing observations. For discrete variables, descriptive statistics will include frequencies and percentages, number of available observations and numbers of missing observations.

We will determine whether there are important baseline differences between the two groups despite randomization with respect to participant characteristics (e.g., gender, race/ethnicity, GA at birth, SGA[<10th percentile]). If any important differences are found, the primary analyses will be repeated after statistically adjusting for these differences. If distributional assumptions associated with a particular statistical procedure are violated, appropriate transformations will be made or non-parametric alternatives will be used (e.g., Wilcoxon rank sum tests in place of two-sample t-tests). Infants enrolled but subsequently found to meet exclusion criteria will be analyzed separately.

The incidence rate of PNAC will be compared between the 2 groups using Kaplan Meier curves. Subjects who reach full enteral feeds before 6 weeks of study period will be censored. Kaplan-Meier (KM) estimates of survival function will be provided and compared between groups. Log-rank test will also be used to compare time to endpoint. Cox proportional hazards model will be fitted after controlling for covariates which are found to be imbalanced in preliminary analysis. Estimate of hazard ratio and associated confidence interval will be obtained.

The potential confounders are sepsis, use of choleric medications and trace elements. Incidence of nosocomial sepsis has decreased remarkably over the last few years in our unit and with

randomization we do not anticipate significant group differences in the incidence of sepsis. The use of choleric medications and discontinuation of trace elements should occur after the development of primary outcome as per the unit policy and therefore these factors are unlikely to confound the relationship between the lipid intake and PNAC.

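### The primary endpoint is inconsistent on sepsis: the PNAC definition in sections I and IV.a implies that a bilirubin rise during sepsis counts, and section V excludes it

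*Combined protocol and SAP*

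**What the plan says.** All references are to the combined protocol and SAP.

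- **Section I (Purpose)** defines PNAC as direct bilirubin of at least 2 mg/dl "in the absence of other known causes of direct hyperbilirubinemia as described under exclusion criteria". **IV.a (Study Design)** repeats this: "in the absence of other known causes of direct hyperbilirubinemia as described in the exclusion criteria".
- **III.4 (Exclusion Criteria)** lists no need for TPN by 72 hours, early direct hyperbilirubinemia, TORCH infections, biliary tract disorders and metabolic disorders. Sepsis is not on the list.
- **Section V (Data Collection)** has clinical data collected "until the subject develops PNAC (direct bilirubin ≥ 2 mg/dl in the absence of concurrent infection". It also defines sepsis as a data item: a positive blood culture, or clinical signs treated with antibiotics for more than 3 days. Concurrent infection is not defined.
- **IV.g (Route, Frequency, and Duration)** gives lipid for "6 weeks or until reach one of the study end points", one of which is that the infant "has direct bilirubin ≥ 2 mg/dl in the absence of sepsis". IV.f has the same sepsis exception.
- **IV.k (Primary Outcome Measures)** says only "in the absence of other known causes (discussed earlier".
- **IV.m**, reason 2, states that "sepsis and prematurity are confounding risk factors". **VII.d** says: "The potential confounders are sepsis, use of choleric medications and trace elements". The only censoring rule in VII.d is for full enteral feeds.
- **VII.a** treats infants whose direct hyperbilirubinemia has a cause other than parenteral nutrition as screen failures and replaces them. **VII.c** puts every randomised subject in the intent-to-treat sample.
- **Section IX** treats a value of 2 mg/dl or more as reaching the primary outcome, with no sepsis exception.

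**The concern.** The primary analysis is a time-to-event comparison, so each infant needs one event indicator and one date. For an infant who first crosses 2 mg/dl while septic, the plan supports different codings in different places. The trial expects few events, so a few such infants could decide the result. With no rule fixed in advance, the coding could be chosen after the data are seen.

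The terms add to the difficulty. Sepsis (IV.f, IV.g) and concurrent infection (V) are not the same condition, and only sepsis is defined. Bilirubin is measured weekly, and no window says how close in time sepsis must be to a measurement to count as concurrent.

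**Working it through.** **1. The sections side by side, for a first value of at least 2 mg/dl during sepsis**

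| Section | Function | Status of the rise |
|---|---|---|
| I, IV.a with III.4 | Definition of PNAC | Event, by implication (sepsis not listed) |
| IV.f, IV.g | End of randomised lipid; IV.g also calls it a study end point | Not an end point |
| IV.k | Primary outcome | Open: refers back without saying to what |
| V | PNAC as used in data collection | Not an event |
| VII.a | Replacement | Infant replaced, if sepsis is taken as a cause other than parenteral nutrition |
| VII.c | Analysis sample | Infant kept |
| VII.d | Analysis | No rule |
| IX | Risk/benefit | Event (no cause exceptions at all) |

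The direct conflict over the term PNAC is section V against sections I and IV.a. A hypothetical infant shows the effect: first value above threshold at week 3 while septic, next one at week 5 without sepsis. Under I and IV.a this is an event at week 3. Under V it is an event at week 5. An analyst who censors at the septic rise records no event, and under VII.a the infant may be replaced.

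**2. The plan's own figures**

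Inputs from section VI: 20 per group, two-sided 0.05, 40% control incidence over 6 weeks, hazard ratio (HR) 3.6, median follow-up 4 weeks, stated power 80.0%.

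Exponential control hazard: −ln(0.6)/6 = 0.0851 per week.

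- Every infant followed 4 weeks: event probabilities 28.9% and 70.7%; events = 20 × (0.289 + 0.707) = 19.9. Schoenfeld power = Φ(½ × √19.9 × ln 3.6 − 1.96) = 81.5%.
- Every infant followed 6 weeks: 40.0% and 84.1%; events = 20 × (0.400 + 0.841) = 24.8. Freedman power = Φ(√24.8 × 2.6/4.6 − 1.96) = 80.4%.

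Both are close to the stated 80%, so the power statement is not at issue. What matters here is that about 20 to 25 events are expected.

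**3. How much the coding could matter (illustration)**

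The documents give no sepsis rate, so the number of septic rises, k, is an assumption. Because k is taken from the events, 2 to 4 rises are about 8% (2/24.8) to 20% (4/19.9) of all events.

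Trials were simulated with the inputs above, 20,000 for each follow-up length (4 or 6 weeks). In each trial k events were labelled septic, and the log-rank test was run with them counted and not counted. Two further choices were varied:

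- Septic events were drawn at random among all events (they carry the lipid effect), or with weights 1 for control and 1/3.6 for the higher-dose arm (independent of lipid).
- Uncounted infants were censored at the rise, or followed event-free to the end.

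Share of trials in which the 0.05 verdict differs, over the 2 × 2 × 2 = 8 combinations:

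| Septic rises (assumed) | Verdict differs |
|---|---|
| 1 | 3.7–9.8% |
| 2 | 4.0–13.1% |
| 4 | 6.1–23.1% |

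Repeat runs agree within simulation error; rounded outward, the ranges are roughly 3–10%, 4–13% and 6–24%. Replacement under VII.a was not simulated.

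Direction for k = 4, 4 weeks, censored: if the rises carry the lipid effect, not counting them loses significance in 11.9% of trials and gains it in 2.5%. If they are independent of lipid, 2.4% lose and 9.1% gain. For k = 2, lipid-independent and followed event-free to 6 weeks, the lean almost disappears: 3.1% lose and 3.9% gain.

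**The case against.** The best defence is that the plan can be read coherently. The sections that mention sepsis or infection at the threshold (IV.f, IV.g and V) all except it, and IV.k looks back after IV.f and IV.g. An analyst could let the specific exception override the general pointer. Calling sepsis a confounder fits this too, since sepsis at another time may still raise risk. Section IX omits every cause exclusion and is probably shorthand. That reading is reasonable, but the plan does not state it, and the definition it repeats points to a list without sepsis.

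Several stronger readings are tempting and are not supported:

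- A reader might infer that sections I and IV.a say outright that a septic rise is PNAC. They do not; it follows only if the exclusion list is taken as complete. The open ending of the TORCH item follows a list of TORCH agents and does not naturally extend to sepsis.
- A reader might take IV.f and IV.g as a full rival endpoint definition. They mainly say when randomised lipid ends; IV.g adds weight only through its term for the end points.
- A reader might conclude that the endpoint cannot be coded. It can, by a choice that the plan leaves open.
- A reader might conclude that the plan's statements on choleretics and trace elements are wrong. Under the policy in IV.j both are triggered at 2 mg/dl with no sepsis exception. If septic rises are not events, these steps could precede the primary outcome, contrary to the expectation in V and VII.d. This holds only under that reading, for an unknown and possibly zero number of infants, and the statements are themselves hedged.

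It may also be said that sepsis is uncommon or balanced by randomisation. VII.d says only that nosocomial sepsis has decreased, and balance between arms does not settle whether a given infant had an event, or when.

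**Conclusion.** The inconsistency is real and lies in the primary endpoint. Section V excludes a rise during infection, sections I and IV.a include it by implication, IV.k does not decide, and VII.a allows removal against the intent-to-treat sample in VII.c. It must be fixed before analysis. That conclusion rests on the text alone.

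The size is unknown. The simulated percentages depend on assumed numbers of septic rises, on exponential hazards with HR 3.6, and on equal follow-up of 4 or 6 weeks. They show only that one to four infants can matter with 20 to 25 events. No loss of power and no direction of bias is claimed: direction depends on whether septic rises carry the lipid effect and on how uncounted infants are followed.

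**What to change.** Before any unblinded analysis:

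1. State one PNAC definition and use it in I, IV.a, IV.k, V and VII.d. It should say whether a rise concurrent with sepsis is an event, is censored, or is not an event with follow-up continuing. Use one term, the section V sepsis definition, and a stated window in days around the weekly bilirubin value. Say how a rise that persists after sepsis is dated.
2. Pre-specify the other definition as a sensitivity analysis.
3. State that randomised infants with a septic rise stay in the intent-to-treat analysis and are not replaced under VII.a.
4. If septic rises are not events, qualify the statements in V and VII.d that place choleretics and trace-element discontinuation after the primary outcome.
5. IV.f and IV.g conflict with IX on whether randomised lipid ends at a rise during sepsis. The investigators must reconcile these sections; no clinical rule is proposed here.

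The cost is protocol and SAP wording and one extra analysis. Sample size and the bilirubin measurement schedule do not change.

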VI. SAMPLE SIZE CALCULATION: Assuming a 4-week median follow-up time and an incidence rate of 40% for 6 weeks in control group, a two-sided log rank test with an overall sample size of 40 subjects (20 per group) achieves 80.0% power at a 0.050 significance level to detect a hazard ratio of 3.6.

Power	Incidence Rate	N Control	N Study	Haz Ratio (HR)
0.8	40%	20	20	3.6
0.8	50%	20	20	3.26
0.8	60%	20	20	3.02

Kaplan-Meier (KM) estimates of survival function will be provided and compared between groups. Log-rank test will also be used to compare time to endpoint. Cox proportional hazards model will be fitted after controlling for covariates which are found to be imbalanced in preliminary analysis. Estimate of hazard ratio and associated confidence interval will be obtained.

VII. DATA ANALYSES AND MONITORING:

a) **Randomization:** Upon successful completion of necessary screening assessments and being confirmed to be eligible by the investigator, subjects will be randomized in 1:1 ratio to two groups: 1) 1 g/kg/day intravenous lipid and 2) 2 g/kg/day intravenous lipid. Each subject will be assigned a unique sequential subject number for identification throughout the entire course of the study. The subject number will not be reused for any other participant in the study. Subjects who are discontinued or withdrawn from the study prior to randomization will be replaced. In addition, subjects who are identified to have direct hyperbilirubinemia from causes other than parenteral nutrition or did not require parenteral nutrition for more than 2 weeks will be considered screen failure and will also be replaced. We anticipate a total number of 52 subjects to participate in the study to complete the study on 40 subjects. During the study, the treatment assignments will be available only to the RP.

c) **Samples for Analysis:** The “Intent-to-Treat” sample includes all subjects who are randomized into the study. Subjects will be grouped according to the treatment to which they are randomized.

d) Statistical Analyses:

General statistical Considerations:

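### Section VI assumes 40% or more control-arm PNAC by 6 weeks, without a source; Section IV(m)3, read as a dose threshold, points to about 19% on 1 g/kg/day, and the Cox analysis has no provision for an arm with few or no events

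*Combined protocol and SAP*

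**What the plan says.** Section VI (Sample Size Calculation) begins "Assuming a 4-week median follow-up time" and "an incidence rate of 40% for 6 weeks in control group". It states that a two-sided log-rank test with 20 infants per group "achieves 80.0% power at a 0.050 significance level" "to detect a hazard ratio of 3.6". Two further rows keep 80% power and 20 per group: 50% incidence with HR 3.26, and 60% with HR 3.02. No row goes below 40%, no source is given for any of the rates, and the control group is not identified with either dose.

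Section IV(m), item 3, draws on the team's observational study: "a mean cumulative dose of 55gm/kg (SD 15) of intravenous lipid is required before the development of PNAC". From this it infers that an infant on 1 g/kg/day "will take ~ 55 days to develop PNAC". It adds that TPN will often last under 42 days, and that some infants in each group are not expected to develop PNAC.

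Sections VI and VII(d) plan Kaplan-Meier curves, a log-rank test and a Cox model adjusted for imbalanced covariates. Of the Cox model they say "Estimate of hazard ratio and associated confidence interval will be obtained". Neither section says what happens if an arm has very few events or none.

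**The concern.** An arm expected to take about 55 days to reach the endpoint would not ordinarily be given a 40% event rate by day 42 without explanation, still less have its sensitivity rows run only upward. The two sections describe different trials: one with a moderate control rate and a hazard ratio between 3.0 and 3.6, the other with a low rate on 1 g/kg/day and a very large contrast between arms.

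Two things are at stake. The first is whether the stated detectable effect can be relied on, since it depends on an unsourced rate. The second is the promised effect estimate. If the 1 g/kg/day arm has few events, an ordinary Cox model may give no finite hazard ratio, and this is most likely when the trial's hypothesis is true.

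**Working it through.** **1. Reproducing Section VI.** Assume exponential hazards, with weekly control hazard λ = −ln(1 − p)/6, 20 infants per arm, and everyone followed 4 weeks. Expected events are d = 20[1 − exp(−4λ)] + 20[1 − exp(−4λ·HR)]. Schoenfeld power is Φ(½√d · ln HR − 1.96).

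| Control rate at 6 weeks | HR | Control + study events | Power |
|---|---|---|---|
| 40% | 3.6 | 5.8 + 14.1 = 19.9 | 81.5% |
| 50% | 3.26 | 7.4 + 15.6 = 23.0 | 80.8% |
| 60% | 3.02 | 9.1 + 16.8 = 26.0 | 80.4% |

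Freedman's formula with 6 weeks of follow-up gives 80.4%, 80.0% and 79.6%. The table is therefore right for its inputs. If control is instead taken as the higher-risk arm, power is only 42–51%, so the table fits 1 g/kg/day as control.

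**2. What Section IV(m)3 gives.** Treat the dose before PNAC as normal with mean 55 and SD 15 g/kg for every infant, and take cumulative dose as daily dose × days (ignoring the initial period at 1 g/kg/day in the higher arm).

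- 1 g/kg/day, 28 days: Φ((28 − 55)/15) = Φ(−1.80) = 3.6%
- 1 g/kg/day, 42 days: Φ((42 − 55)/15) = Φ(−0.87) = 19.3%
- 1 g/kg/day, 49 days, if lipid continued at that rate: Φ((49 − 55)/15) = Φ(−0.40) = 34.5%
- 2 g/kg/day, 28 days: Φ((56 − 55)/15) = 52.7%
- 2 g/kg/day, 42 days: Φ((84 − 55)/15) = 97.3%

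The figure to set against 40% at 6 weeks is 19.3%. It hardly depends on shape: a gamma with the same mean and SD gives 19.7%, a lognormal 19.1%. The 28-day figure of 3.6% has its own counterpart under Section VI: 1 − 0.6^(4/6) = 29%. With SD 15, a 40% rate by 42 g/kg would need a mean of about 46 g/kg.

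The implied ratio of cumulative hazards at 42 days is ln(1 − 0.973)/ln(1 − 0.193) = 16.8, against 3.0–3.6 in the table.

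**3. Power.** In simulations of 4,000 trials per scenario under the threshold model, log-rank power is 97–98% with follow-up of about 4 weeks and about 100% if all infants are followed to 42 days. If 19.3% is used but HR stays at 3.6, events fall to 10.7 and power to 55% (4 weeks), or to 14.6 events and 69% (6 weeks).

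**4. Events in the 1 g/kg/day arm under the threshold model.**

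| Follow-up | Expected events | Chance of none |
|---|---|---|
| All followed 4 weeks | 20 × 0.036 = 0.7 | 0.964^20 = 48% |
| Censoring uniform, 2–6 weeks | 1.1 | 31% |
| Censoring up to 42 days, median observed time (events included) about 4 weeks | 2.1–2.3 | about 10% |
| All followed 42 days | 20 × 0.193 = 3.9 | 0.807^20 = 1.4% |

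The Cox estimate can also diverge when the arm has events but they fall only after no 2 g/kg/day infant remains at risk. Counting those cases, the simulated chance of an infinite hazard ratio is 48% for the first row, 39% for the second and 3.5% for the last.

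**5. Detectable hazard ratio at lower rates.** Solving the step 1 formula for 80% power (n = 40, 4 weeks) gives HR 6.6 at 10%, 4.8 at 20% and 4.0 at 30%.

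**The case against.** The strongest reply is that Section IV(m)3 does not state an incidence. It does not say whether 55 (SD 15) describes all infants or only those who developed PNAC; if only cases, no rate follows. The normal shape is also added here. Mean and SD alone bound the proportion at or below 42 g/kg only at 225/(225 + 169) = 57%, so 40% is not strictly excluded. The plan treats PNAC as multifactorial, and a lipid-only threshold omits events from other causes. All of this stands. It is partly offset because Section IV(m)3 itself applies the 55 g/kg figure to any infant on 1 g/kg/day.

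Other passages favour a higher rate. Section II reports neonatal incidence up to 84% and nearly universal PNAC by 6 weeks on TPN. Section VII(a) replaces infants who need parenteral nutrition for no more than 2 weeks. The outcome window in Section IV(k) extends a week past the 6-week period, and the 49-day figure of about 34% is near 40%. These may explain the upward rows, but Section VI does not invoke them.

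A reader might infer that the trial is underpowered. The documents do not support that: the same threshold figures predict a much larger contrast and higher log-rank power. The 55–69% result joins a rate from one section to a hazard ratio from the other. The added lower-incidence rows are likewise a sensitivity display, not a forecast.

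The sparse-event risk also depends on what a 4-week median means. If it is observed time shortened by events, the chance of no event in the 1 g/kg/day arm is nearer 10% than 48%. The log-rank test still works with no events in one arm.

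**Conclusion.** The point holds as an unreconciled planning assumption, not as an arithmetic error. If 1 g/kg/day is the control arm and 55 (SD 15) is a roughly normal threshold for all infants, the 6-week control rate is about 19% rather than 40–60%, and the contrast is far larger than the table's hazard ratios. Neither assumption is stated in the plan, so the two sections are in tension rather than proven incompatible.

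A reader might also conclude that the hazard ratio will be inestimable. That goes too far. The chance of no event in the 1 g/kg/day arm runs from about 1% (all followed to 42 days) to 48% (all followed 4 weeks), and is about 10–48% with a median near 4 weeks. Where it happens, the planned Cox estimate is infinite and its Wald interval uninformative. That is enough to justify a prespecified method, and not enough to call the primary comparison unsound.

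**What to change.** - **Reconcile Sections IV(m)3 and VI.** Name the control arm, give the source of the 40–60% rates, and state whether 55 g/kg (SD 15) describes all infants or only PNAC cases.
- **Extend the Section VI table downward.** Add 10%, 20% and 30% rows, with detectable hazard ratios of about 6.6, 4.8 and 4.0 at 80% power (n = 40, 4-week follow-up).
- **Sections VI and VII(d).** Keep the log-rank test. Prespecify Firth-penalised Cox regression with profile-likelihood intervals for the hazard ratio, so that an estimate exists if one arm has no events.

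The cost is a few sentences, three table rows and one software option. The stated detectable effect becomes less favourable. No infants are added.
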